6.5.5.2 Management of non-hematological toxicity

Repeat dose interruptions are allowed as required, for a maximum of 4 weeks on each occasion. If the interruption is any longer than this the study monitor must be informed. Where toxicity reoccurs following re-challenge with study treatment, and where further dose interruptions are considered inadequate for management of toxicity, then the patient should be considered for dose reduction or must permanently discontinue study treatment.

Study treatment can be dose reduced to 250 mg twice daily as a first step and to 200 mg twice daily as a second step. Treatment must be interrupted if any NCI-CTCAE grade 3 or 4 adverse event occurs which the investigator considers to be related to administration of study treatment.

Management of new or worsening pulmonary symptom

If new or worsening pulmonary symptoms (e.g., dyspnea) or radiological abnormalities occur in the absence of a clear diagnosis, an interruption in study treatment dosing is recommended and further diagnostic workup (including a high resolution CT scan) should be performed to exclude pneumonitis.

Following investigation, if no evidence of abnormality is observed on CT imaging and symptoms resolve, then study treatment can be restarted, if deemed appropriate by the investigator. If

significant pulmonary abnormalities are identified, these need to be discussed with the Study Physician.

Management of nausea and vomiting

Events of nausea and vomiting are known to be associated with olaparib treatment. These events are generally mild to moderate (CTCAE grade 1 or 2) severity, intermittent and manageable on continued treatment. The first onset generally occurs in the first month of treatment for nausea and within the first 6 months of treatment for vomiting. For nausea, the incidence generally plateaus at around 9 months, and for vomiting at around 6 to 7 months.

No routine prophylactic anti-emetic treatment is required at the start of study treatment, however, patients should receive appropriate anti-emetic treatment at the first onset of nausea or vomiting and as required thereafter, in accordance with local treatment practice guidelines. Alternatively, olaparib tablets can be taken with a light meal/snack (ie 2 pieces of toast or a couple of biscuits).

As per international guidance on anti-emetic use in cancer patients (ESMO, NCCN), generally a single agent antiemetic should be considered eg. dopamine receptor antagonist, antihistamines or dexamethasone.

Interruptions for intercurrent non-toxicity related events

Study treatment dose interruption for conditions other than toxicity resolution should be kept as short as possible. If a patient cannot restart study treatment within 4 weeks for resolution of intercurrent conditions not related to disease progression or toxicity, the case should be discussed with the Primary Investigator.

All dose reductions and interruptions (including any missed doses), and the reasons for the reductions/interruptions are to be recorded in the eCRF.

Study treatment should be stopped at least 3 days prior to planned surgery. After surgery study treatment can be restarted when the wound has healed. No stoppage of study treatment is required for any needle biopsy procedure.

Study treatment should be discontinued for a minimum of 3 days before a patient undergoes radiation treatment. Study treatment should be restarted within 4 weeks as long as any bone marrow toxicity has recovered.

Because the AEs related to olaparib may include asthenia, fatigue and dizziness, patients should be advised to use caution while driving or using machinery if these symptoms occur.

Table 12 Dose reductions for study treatment

Initial Dose	Following re-challenge post interruption: Dose reduction 1	Dose reduction 2
300 mg twice daily	250 mg twice daily	200 mg twice daily

6.5.5.3 Renal impairment

If subsequent to study entry and while still on study therapy, a patient's estimated CrCl falls below the threshold for study inclusion (≥ 51 ml/min), retesting should be performed promptly.

A dose reduction is recommended for patients who develop moderate renal impairment (calculated creatinine clearance by Cockcroft-Gault equation or based on a 24 hour urine test of between 31 and 50 ml/min) for any reason during the course of the study: the dose of olaparib should be reduced to 200 mg twice daily.

Because the CrCl determination is only an estimate of renal function, in instances where the CrCl falls to between 31 and 50 mL/min, the investigator should use his or her discretion in determining whether a dose change or discontinuation of therapy is warranted.

Olaparib has not been studied in patients with severe renal impairment (creatinine clearance ≤ 30 ml/min) or end-stage renal disease; if patients develop severe impairment or end stage disease is it recommended that <<select olaparib or study treatment>> be discontinued.

6.6 Genetics

6.6.1 Collection of mandatory genetic samples

The patient's consent to participate in the genetic research components of the study is mandatory.

The tissue sample for genetic research will be obtained from the patients from archival tissue or from metastatic biopsy during pre-screening period and post-treatment.

Samples will be collected, labelled, stored and shipped as detailed in the Laboratory Manual.

Genetic signatures indicating homologous recombination deficiency will be analyzed. This analysis is required to include the patient in the study.

6.7 Biomarkers

Optional samples for biomarker research that should be collected from patients in the study where possible are the following:

- Tumor biopsies will be taken at baseline and at progression for investigation of genetic signatures and transcriptome analysis to evaluate their association with the observed clinical responses to olaparib.
- Please refer to the Laboratory Manual for further details regarding blood sample collection, shipping and storage.

In addition, blood will be collected, and analysis may be performed on exploratory biomarkers thought to play a role in homologous recombination deficiency including, but not limited to,

genome-wide analysis for RNA, serum analytes, or tissue biomarkers to evaluate their association with observed clinical responses to olaparib.

Other samples may be used for research to develop methods and further refine assays for predicting response to olaparib and clarifying mechanisms of resistance. All samples will be collected at the timepoints indicated in the SoA. Details regarding the collection, processing, shipping, and storage of samples for exploratory research will be defined in the Laboratory Manual.

6.7.1 Storage, re-use and destruction of biomarker samples

Samples will be stored for a maximum of 5 years from the date of the Last Patient's Last Visit, after which they will be destroyed. Samples will be stored at the University of Washington and/or Fred Hutchinson Cancer Research Center (UW/FHCRC). These samples may also be sent to our research partners participating in this study, including Astra Zeneca. Specimens will not be used for reasons unrelated to this research study. All specimens will be kept in locked research laboratories at UW/FHCRC. The Sponsor Investigator will supervise the use of these specimens. The results of this biomarker research will be reported either in the CSR itself or as an addendum, or separately in a scientific report or publication. Statistical Considerations

6.8 Sample size determination

Based on the PROFOUND study, we estimate a response rate of 20% (H0) in patients with any HR mutations (e.g. BRCA2, ATM, CDK12, CHEK2, etc).² We will require a 50% (H1) response rate in iHRD positive patients to justify further development of this approach for selecting patients for olaparib treatment. Therefore, assuming we enroll 20 iHRD positive patients, this study would provide 87% power at a one-sided alpha of 0.03 to detect a 50% response rate compared to the null rate of 20%. Given that prior experience has shown that ~75% of patients with a positive LOH score will also have evidence of iHRD positivity, we will enroll a total of 30 patients to identify at least 22 iHRD positive subjects. This should allow for a drop out rate of 10% to ensure that at least 20 iHRD positive subjects are able to reach 12 weeks of treatment for the primary endpoint analysis.

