Based on the PROFOUND study, we estimate a response rate of 20% (H0) in patients with any HR mutations (e.g. BRCA2, ATM, CDK12, CHEK2, etc).² We will require a 50% (H1) response rate in iHRD positive patients to justify further development of this approach for selecting patients for olaparib treatment. Therefore, assuming we enroll 20 iHRD positive patients, this study would provide 87% power at a one-sided alpha of 0.03 to detect a 50% response rate compared to the null rate of 20%. Given that prior experience has shown that ~75% of patients with a positive LOH score will also have evidence of iHRD positivity, we will enroll a total of 30 patients to identify at least 22 iHRD positive subjects. This should allow for a drop out rate of 10% to ensure that at least 20 iHRD positive subjects are able to reach 12 weeks of treatment for the primary endpoint analysis.

[figure not shown]
The primary objective is to determine the percentage of patients who are iHRD+ that achieve a PSA₅₀ response (i.e. $\geq 50\%$ decline in PSA from baseline). The lowest on treatment PSA will be defined as the lowest value following at least 12 weeks of treatment (i.e. the beginning of Cycle 4). The PSA₅₀ response rate will be calculated along with 90% confidence intervals (CI). PSA changes will be presented as waterfall plots per PCWG3 recommendations. If a patient drops out

of the study prior to assessing best PSA response he will be considered as not having had a PSA50 response. However, an additional study subject will be enrolled to ensure an adequate number of subjects are available to estimate the PSA50 response rate.

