6.9 Statistical analyses

6.9.1 Efficacy analyses

Primary Objective

The primary objective is to determine the percentage of patients who are iHRD+ that achieve a PSA₅₀ response (i.e. $\geq 50\%$ decline in PSA from baseline). The lowest on treatment PSA will be defined as the lowest value following at least 12 weeks of treatment (i.e. the beginning of Cycle 4). The PSA₅₀ response rate will be calculated along with 90% confidence intervals (CI) using Wilson's method. PSA changes will be presented as waterfall plots per PCWG3 recommendations. If a patient drops out of the study prior to assessing best PSA response he will be considered as not having had a PSA₅₀ response.

ORR Response

For patients with measurable disease, ORR will be defined as a 30% decrease from baseline per RECIST 1.1 criteria at any time point. The percent of patients with ORR and 90% CI, calculated using Wilson's method, will be provided. Radiographic responses will be presented as waterfall plots.

rPFS, PSA PFS, OS

These endpoints are defined in section 3.5. The distributions of each endpoint will be estimated using the Kaplan-Meier method. Median times to event will be reported with 90% CIs using linear interpolation between steps of the survival curve.

Exploratory Objectives

Response rates and time to event endpoints as described above will be compared between patients who are iHRD+ and iHRD-. PSA and radiographic response rates including percentage and 90% CIs, calculated using Wilson's method, will be reported. Differences in response rates will be quantified using logistic regression with no additional adjustment. Time to event endpoints will be compared with log-rank tests.

If dropout is greater than anticipated, primary and secondary endpoint analyses will still be based on patients with 12 weeks of follow-up. However, the exploratory analysis will examine extreme scenarios in which endpoints for dropouts are imputed to minimize differences between iHRD+ and iHRD- patients.

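### The primary PSA50 analysis has two incompatible dropout rules, and the planned iHRD+ counts of 22 and 20 are averages presented as secured

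*Combined protocol and SAP*

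**What the plan says.** **Dropouts.** Under Primary Objective, Section 6.9.1 says: "If a patient drops out of the study prior to assessing best PSA response he will be considered as not having had a" PSA50 response. The Synopsis (Section 1.2, Statistical Methods) has the same rule. Under Exploratory Objectives, Section 6.9.1 then says: "If dropout is greater than anticipated, primary and secondary endpoint analyses will still be based on patients with 12 weeks of follow-up". The sentence after that one reserves imputation of dropouts for the exploratory analysis.

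**Replacement.** Only the Synopsis adds that, after a dropout, "an additional study subject will be enrolled to ensure an adequate number of subjects are available". Sections 6.8 and 6.9.1 do not mention replacement.

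**Counts and power.** Section 6.8, like the Synopsis, sets the null as "we estimate a response rate of 20% (H0) in patients with any HR mutations" and the target as "We will require a 50% (H1) response rate in iHRD positive patients". It says: "assuming we enroll 20 iHRD positive patients, this study would provide 87% power at a one-sided alpha of 0.03". It takes about 75% of LOH-positive patients to be iHRD+, so "we will enroll a total of 30 patients to identify at least 22 iHRD positive subjects". It allows 10% dropout "to ensure that at least 20 iHRD positive subjects are able to reach 12 weeks of treatment".

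**The concern.** The two dropout rules give different denominators for the same primary rate. If the 12-week sentence is the standing rule, it contradicts the non-responder rule. If it is a conditional override, the observed dropout rate selects the denominator, and the more favourable one applies when dropout is high. Sections 1.2 and 4.1 take patients off study for clinical or radiographic progression at any time, so losses before week 12 may include early failures. Removing them would inflate the PSA50 rate.

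The second issue is smaller. The sample-size text presents average counts as secured, so a reader cannot see how likely the study is to reach the 20 patients for whom power is quoted.

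**Working it through.** **Inputs.** From Section 6.8: null rate 0.20, target rate 0.50, 20 iHRD+ patients, 87% power, one-sided alpha 0.03, yield 0.75, 30 enrolled, dropout 0.10. From Section 6.9.1: 90% Wilson interval.

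**1. The plan's own figures.** 20 / 0.9 / 0.75 = 29.6, so 30 enrolled. With success at 8 or more of 20, P(X ≥ 8 | 20, 0.5) = 0.868 and P(X ≥ 8 | 20, 0.2) = 0.032. The 87% and 0.03 reproduce after rounding.

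**2. The two dropout rules.** Assumed illustration: 22 iHRD+ patients, 4 dropouts. With z = 1.645, the Wilson lower limit is [p + z²/2n − z√(p(1−p)/n + z²/4n²)] / (1 + z²/n).

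| Responders | Rule | Rate | 90% Wilson CI | Exact one-sided p against 20% |
|---|---|---|---|---|
| 7 | dropouts as non-responders | 7/22 = 31.8% | 18.3–49.4% | 0.133 |
| 7 | 12-week patients only | 7/18 = 38.9% | 22.7–58.0% | 0.051 |
| 8 | dropouts as non-responders | 8/22 = 36.4% | 21.9–53.8% | 0.056 |
| 8 | 12-week patients only | 8/18 = 44.4% | 27.2–63.1% | 0.016 |

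With 7 responders, the plan's own interval includes 20% under one rule and excludes it under the other. With 8 responders, both intervals exclude 20%. Only the exact p-values then fall on either side of 0.03.

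**3. The counts.** Expected iHRD+: 30 × 0.75 = 22.5. Expected at 12 weeks: 22.5 × 0.9 = 20.25. Without replacement:

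| Yield | P(at least 22 iHRD+) = P(Bin(30, yield) ≥ 22) | P(at least 20 at 12 weeks) = P(Bin(30, 0.9 × yield) ≥ 20) |
|---|---|---|
| 70% | 0.432 | 0.417 |
| 75% | 0.674 | 0.623 |
| 80% | 0.871 | 0.806 |

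With replacement, at 75% yield and 10% dropout, the probability of at least 20 at 12 weeks depends on the reading:
- One replacement per iHRD+ dropout, LOH-positive with unknown iHRD status and able to drop out: 0.825.
- Every iHRD+ dropout fully made good: P(Bin(30, 0.75) ≥ 20) = 0.894.
- Every dropout, iHRD+ or not, replaced by an iHRD+ patient who completes 12 weeks: P(Bin(30, 0.75 + 0.25 × 0.10) ≥ 20) = P(Bin(30, 0.775) ≥ 20) = 0.944.

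**4. Power averaged over the random iHRD+ count.** Assumptions: count distributed Bin(30, 0.75), all iHRD+ patients analysed, dropouts as failures, no replacement. The cut-off at each n is the smallest with exact alpha at most 0.0325, a cap chosen here so that 8 of 20 is retained.
- If 50% is the rate in all iHRD+ patients: 0.858 (0.845 with a strict cap of 0.03).
- If 50% is the rate in 12-week patients only, the overall rate is 0.5 × 0.9 = 45%: 0.727 (0.709 with the strict cap).

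**The case against.** The best defence is that the design is sound and the wording is loose. The figures reproduce, the text is hedged (an approximate yield, an allowance for dropout), and inflating enrolment by expected yield and dropout is ordinary practice. A shortfall of one is mild: 19 analysed patients, with success at 8 or more, still have 82% power. All of this stands, and it is why the counts are the secondary issue. It does not reconcile the two dropout rules.

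Several stronger readings are tempting, but the documents do not support them.
- *The study is underpowered or its arithmetic is wrong.* Average power is about 86% when the 50% is taken, as Section 6.8 words it, as the rate in iHRD+ patients. Requiring a strict 0.03 (9 of 20, power 0.75) presses on a rounded figure.
- *The switch to 12-week patients would occur in 38% of trials.* P(more than 2 dropouts of 22) is 0.38 at a true 10%, but the plan gives no threshold for dropout greater than anticipated. With a threshold one dropout higher, the figure is 17%. That is also the chance of 4 or more dropouts, as in the illustration, which is possible but not typical.
- *The 8-responder case reverses the plan's conclusion.* It does so only on an exact test, which Section 6.9.1 does not name for the primary rate.
- *Replacement caps the probability at 89%.* That holds only if iHRD+ dropouts alone are replaced. The Synopsis does not say so. Nor do the documents agree on when iHRD status is known: Section 4.1 puts sequencing after enrolment, Section 6.1.2 and the Schedule of Activities put it at screening, and Section 6.6.1 makes HRD signature analysis a condition of inclusion.
- *The plan has no success cut-off.* The text gives none, but a figure directly after the sample-size text in the Synopsis is not shown and may contain it.

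**Conclusion.** The inconsistency is real and should be resolved before the primary analysis. Section 6.9.1 both keeps early dropouts in the PSA50 denominator and, when dropout is high, removes them. In the assumed case of 4 dropouts among 22, the rate moves by about 7 percentage points with 7 responders and 8 with 8, and with 7 the plan's own interval changes sides of the 20% null. How often this would matter cannot be computed, because the trigger is undefined.

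The counts are expected values. At exactly 75% yield and 10% dropout, the 12-week target of 20 is met with probability of about 62% without replacement (42% to 81% for yields of 70% to 80%). With replacement it is about 82–89% if only iHRD+ dropouts are replaced, and up to about 94% on the broadest reading. The 87% power is correct for 20 analysed patients with success at 8 or more. Average power is about 86%, or about 73% if the 50% was meant only for patients who reach 12 weeks.

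**What to change.** 1. In the Synopsis and Section 6.9.1, use one primary rule: all treated iHRD+ patients, with dropouts before best PSA counted as non-responders. Move the analysis of patients with 12 weeks of follow-up to a sensitivity analysis.
2. Carry the Synopsis replacement rule into Sections 6.8 and 6.9.1, saying who is replaced, by whom and how often, or delete it. If it is kept, state that a replaced dropout still counts as a non-responder.
3. In the Synopsis and Section 6.8, describe the counts as expected, for example: *30 LOH-positive patients are expected to give 22.5 iHRD+ patients and 20.3 at 12 weeks; at exactly 75% yield and 10% dropout, the probability of at least 20 at 12 weeks is about 62% before any replacement (42% to 81% for yields of 70% to 80%).*
4. Label the 87% as conditional on 20 analysed patients, success at 8 or more, exact one-sided alpha 0.032. Say whether the 50% applies to all iHRD+ patients (average power about 86%) or to 12-week patients only (about 73%).
5. The sponsor should confirm the success cut-off for the iHRD+ number actually reached, unless the figure not shown already gives it.

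The changes are to wording and add no patients. The cost is less favourable stated figures and a lower observed PSA50 rate when dropout is high. If the 50% was meant for 12-week patients, the plan would also have to acknowledge power of about 73% under the recommended denominator.

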6.9 Statistical analyses

6.9.1 Efficacy analyses

Primary Objective

The primary objective is to determine the percentage of patients who are iHRD+ that achieve a PSA₅₀ response (i.e. $\geq 50\%$ decline in PSA from baseline). The lowest on treatment PSA will be defined as the lowest value following at least 12 weeks of treatment (i.e. the beginning of Cycle 4). The PSA₅₀ response rate will be calculated along with 90% confidence intervals (CI) using Wilson's method. PSA changes will be presented as waterfall plots per PCWG3 recommendations. If a patient drops out of the study prior to assessing best PSA response he will be considered as not having had a PSA₅₀ response.

ORR Response

For patients with measurable disease, ORR will be defined as a 30% decrease from baseline per RECIST 1.1 criteria at any time point. The percent of patients with ORR and 90% CI, calculated using Wilson's method, will be provided. Radiographic responses will be presented as waterfall plots.

rPFS, PSA PFS, OS

These endpoints are defined in section 3.5. The distributions of each endpoint will be estimated using the Kaplan-Meier method. Median times to event will be reported with 90% CIs using linear interpolation between steps of the survival curve.

Exploratory Objectives

Response rates and time to event endpoints as described above will be compared between patients who are iHRD+ and iHRD-. PSA and radiographic response rates including percentage and 90% CIs, calculated using Wilson's method, will be reported. Differences in response rates will be quantified using logistic regression with no additional adjustment. Time to event endpoints will be compared with log-rank tests.

If dropout is greater than anticipated, primary and secondary endpoint analyses will still be based on patients with 12 weeks of follow-up. However, the exploratory analysis will examine extreme scenarios in which endpoints for dropouts are imputed to minimize differences between iHRD+ and iHRD- patients.

We will additionally be looking at association between response rate and different predictors of homologous recombination deficiency including large scale state-transition (LST) score, COSMIC signature 3/8, and presence of underlying HR mutation. We will report the presence of underlying HR mutations in both the iHRD(+) and iHRD(-) groups. Depending on the final makeup of the study population, we will report PSA and radiographic response rates among various subsets which may include iHRD(+) and *BRCA* mutant iHRD(-) patients. We will also use the results of this trial to optimize iHRD classification framework and develop a clinical pipeline for calling iHRD from targeted exome panels. We will also describe the results of transcript profiling studies from tumor biopsies and compare pre and post treatment profiles.

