4.2 Scientific rationale for study design

Overall rationale and study population:

The purpose of this study is to explore the efficacy of using a functional method of calling HRR deficiency (HRD) to predict response to olaparib. Men with mCRPC will be eligible if they have a positive LOH score on metastatic tissue and/or cell-free circulating tumor DNA (ctDNA), which has been associated with response to PARP inhibition¹⁰. They are eligible for inclusion into the study if they have progressed on abiraterone or enzalutamide, which is in concordance with the current population for which olaparib is indicated.

Study design:

This is a single arm, Phase II study designed to provide an initial estimate of clinical activity of olaparib in mCRPC patients that have iHRD+ tumors. Because there is no control group this study will not be blinded.

Primary and secondary outcome measures:

Lowest on-treatment PSA was chosen as a primary endpoint, as decline in PSA is generally associated with tumor control and can be assessed as early as 12 weeks. Radiographic response rate was not chosen as many prostate cancer patients have primarily osseous metastases and are not evaluable per RECIST criteria. This study follows the PCWG3 criteria for assessing PSA and defining PSA progression¹. Secondary outcomes included are also reflective of PCWG3 guidelines.

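### The rule behind alpha 0.03 and 87% power (at least 8 of 20 responders) is not written, and the 50% requirement, 90% interval and dropout rules do not match it

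*Combined protocol and SAP*

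**What the plan says.** Section 6.8, repeated in the synopsis under Statistical Methods, sets the null: "we estimate a response rate of 20% (H0) in patients with any HR mutations". It then says: "We will require a 50% (H1) response rate in iHRD positive patients to justify further development of this approach". With 20 iHRD+ patients, "this study would provide 87% power at a one-sided alpha of 0.03". The plan is to enrol 30 patients, identify at least 22 who are iHRD+, allow 10% dropout, and have at least 20 reach 12 weeks.

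Section 6.9.1 gives the primary analysis. The PSA50 "response rate will be calculated along with 90% confidence intervals (CI) using" Wilson's method, and PSA changes go into waterfall plots. It gives no test, p-value or responder count, and no comparison with 20%. The synopsis gives the same 90% interval without naming the method. Section 4.2 describes the study as "designed to provide an initial estimate of clinical activity of olaparib" in iHRD+ disease.

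Three sentences bear on who is analysed:
- Section 6.9.1, primary objective: "If a patient drops out of the study prior to assessing best PSA response he will be considered as not having had" a PSA50 response.
- Section 6.9.1, under the exploratory objectives: "If dropout is greater than anticipated, primary and secondary endpoint analyses will still be based on patients with 12 weeks of follow-up".
- Synopsis only: "an additional study subject will be enrolled to ensure an adequate number of subjects are available to estimate" the PSA50 rate.

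**The concern.** An alpha and a power belong to a decision rule. Here both are stated, with a sentence on what would justify further development, but the rule that produces them is not in the readable text. A reader looking for it finds two candidates, the 50% requirement and the 90% interval, and neither has the stated operating characteristics.

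The trial is open-label and single-arm. If the rule and the denominator are settled only after the responses are known, the bar can move by a responder, and the claimed alpha and power no longer describe the decision taken.

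**Working it through.** Inputs from section 6.8: p0 = 0.20, p1 = 0.50, n = 20 analysed, one-sided alpha 0.03, power 0.87, 22 iHRD+ patients before dropout. From section 6.9.1: a 90% Wilson interval, so z = 1.645 and a nominal 5% per tail.

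**Step 1: reproduce the plan.** For the rule of at least r responders among n, alpha = P(X ≥ r) with X ~ Bin(n, 0.20), and power = P(X ≥ r) with X ~ Bin(n, 0.50).

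| Rule | Alpha | Power |
|---|---|---|
| ≥ 7/20 | 0.0867 | 0.942 |
| ≥ 8/20 | 0.0321 | 0.868 |
| ≥ 9/20 | 0.0100 | 0.748 |
| ≥ 10/20 | 0.0026 | 0.588 |
| ≥ 8/22 | 0.0561 | 0.933 |
| ≥ 9/22 | 0.0201 | 0.857 |
| ≥ 11/22 | 0.0016 | 0.584 |

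At n = 20 only 8 gives both stated figures, with alpha matching 0.03 after rounding. The n = 22 powers apply the 50% rate to all 22 patients.

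**Step 2: the 50% requirement read literally.** An observed rate of 50% is 10/20, with power 58.8%, or 11/22, with power 58.4%. Neither is compatible with 87%.

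**Step 3: the Wilson interval, if it were used as the rule.** Its lower limit exceeds 0.20 exactly when (x/n − 0.20)/√(0.20 × 0.80/n) exceeds 1.645.
- n = 20, standard error √(0.16/20) = 0.0894: 6/20 gives 0.10/0.0894 = 1.12 (no); 7/20 gives 0.15/0.0894 = 1.68 (yes; lower limit 0.2023).
- n = 22, standard error √(0.16/22) = 0.0853: 7/22 gives 0.118/0.0853 = 1.39 (no); 8/22 gives 0.164/0.0853 = 1.92 (yes; lower limit 0.2187).

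The first passing counts are therefore 7/20 (alpha 8.7%, power 94.2%) and 8/22 (alpha 5.6%, power 93.3%).

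**Step 4: how often this matters.** If the 50% is only the design alternative, the Wilson reading and the 8/20 rule differ only at exactly 7/20. P(X = 7) is 0.0867 − 0.0321 = 0.055 at a true rate of 20% and 0.942 − 0.868 = 0.074 at 50%. At 35%, an assumed intermediate rate that is not in the documents, it is 0.184.

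**Step 5: the denominator.** Take 22 iHRD+ patients, 3 dropouts (3/22 = 13.6%, above the planned 10%) and 8 responders; these counts are an illustration.
- Dropouts kept as non-responders: 8/22, P(X ≥ 8 | 22, 0.20) = 0.056. This misses the cut-off of 9.
- Only patients with 12 weeks of follow-up: 8/19, P(X ≥ 8 | 19, 0.20) = 0.023. This is below 0.03.

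Section 6.9.1 supports both. The synopsis would also add replacement subjects while still counting the dropouts as failures, which changes the number analysed again.

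**The case against.** The design is complete enough for its rule to be recovered. Null, alternative, n, sidedness, alpha and power are all given, and at n = 20 only one count fits them. The Wilson interval is never compared with 20%. The same 90% level is used for ORR, medians and exploratory rates, so it looks like a reporting convention, and it suits a study described in 4.2 as giving an initial estimate. The 50% carries the label (H1), and the next sentence goes on from it to power the study to detect 50% against 20%. The synopsis has a figure after the sample-size text that is not shown; what it contains is unknown. The analysis-set conflict would need repair even if a cut-off were written.

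Most of this stands, and it rules out three stronger conclusions that a reader might draw:
- *The sample size or power is wrong.* It is not; it reproduces.
- *The trial will run at a type I error of 8.7%.* The documents do not make the interval a decision rule, and n = 22 gives 5.6%.
- *Bars of 7, 8 and 10 of 20 are all equally live, so the readings conflict anywhere from 7 to 9 responders.* That range would have probability 35% at a true rate of 50%, but it depends on the literal 50% reading, which the (H1) label and the 87% figure both disfavour.

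The objection does not remove the gap. A plan that claims 87% power and sets a requirement for further development should state the rule, and the operative sections 6.8 and 6.9.1 give none in their text and have no missing figure. The two dropout sentences in 6.9.1 contradict each other on any reading.

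**Conclusion.** The point holds as a mismatch in what is written. The sample-size calculation is correct under an unstated rule of at least 8/20 (alpha 0.032, power 86.8%). The 50% sentence read literally contradicts the stated power (58.8%), and the 90% interval, if it were used to decide, would be one responder more lenient. If the 50% is only the design alternative, the disagreement is confined to 7/20: about 5% probability at a true rate of 20% and 7% at 50%. The dropout contradiction needs no such assumption, and the same 8 responders can fall on either side of the bar.

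The figures assume exact binomial responses with a common rate. It remains possible that the synopsis figure not shown contains the cut-off; if so, it should be repeated in 6.9.1. This should be fixed before the responses are analysed.

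**What to change.** In the synopsis and section 6.9.1:
- Name an exact one-sided binomial test against 20% as the primary test. Success is at least 8/20, with attained alpha 0.032 and power 86.8% stated; if 22 are analysed, at least 9/22 (alpha 0.020, power 85.7% if the 50% rate applies to all 22).
- State that the 90% Wilson interval is descriptive.
- State that the 50% in 6.8 is the design alternative. If it is meant as an observed-rate threshold, correct the power to about 59%.
- Define one primary analysis set: all treated iHRD+ patients, with dropouts as non-responders. Delete the 12-week-follow-up sentence or demote it to a sensitivity analysis, and align the replacement sentence with this set.

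The cost is protocol wording only, with three consequences to accept openly. One more responder is needed than under the Wilson reading. The attained alpha is 0.032; a strict limit of 0.03 would need 9/20, with power 75%. Counting dropouts as failures lowers power: if 2 of 22 drop out and the other 20 respond at 50%, reaching 9 has probability P(X ≥ 9 | 20, 0.50) = 74.8%, not 85.7%.
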